## **2. CORE PROTOCOL**

### **2.1 OBJECTIVES AND HYPOTHESES**

#### **2.1.1 Primary Objectives**

1. To assess the safety and tolerability of V212 when administered to adults with STM .
2. To assess the impact of V212 on the development of HZ in adults with STM.

#### **2.1.2 Primary Hypotheses**

Vaccination with V212 will reduce the incidence of HZ compared with placebo in adults with STM. The following hypothesis will be tested at the end of the study in the STM population.

- 1) The statistical criterion for success requires that the lower bound of the 97.5% (one-sided  $\alpha=0.0125$ ) confidence interval (CI) for the estimated vaccine efficacy in adults with STM be greater than 25%.

#### **2.1.3 Secondary Objectives**

1. To assess the impact of V212 on the development of moderate to severe HZ-associated pain at any time from HZ onset through the end of the 6 month HZ follow-up period. Moderate to severe HZ-associated pain is defined as 2 or more occurrences of a score of 3 or greater (0-to-10 scale) on the Zoster Brief Pain Inventory (ZBPI).
2. To assess the impact of V212 on the development of HZ complications defined as the occurrence of any of the following during the study: hospitalization or prolongation of hospitalization due to HZ, disseminated HZ (including disseminated HZ rash or VZV viremia), visceral HZ, ophthalmic HZ, neurological impairment due to HZ, or administration of intravenous acyclovir therapy for treatment of HZ.
3. To assess the impact of V212 on the development of PHN. PHN is defined as a worst pain score (in the previous 24 hours) of 3 or greater (0-to-10 scale) on the ZBPI, that persists or appears greater than or equal to 90 days after the onset of HZ rash.

The above objectives will be evaluated for STM only.

#### **2.1.4 Exploratory Objectives**

1. To assess the safety and tolerability of V212 when administered to adults with HM.
2. To assess the impact of V212 on the development of HZ in adults with HM.
3. To assess the impact of V212 on the development of moderate to severe HZ-associated pain at any time from HZ onset through the end of the 6 month HZ follow-up period. Moderate to severe HZ-associated pain is defined as 2 or more occurrences of a score of 3 or greater (0-to-10 scale) on the Zoster Brief Pain Inventory (ZBPI) in adults with HM.

4. To assess the impact of V212 on the development of HZ complications defined as the occurrence of any of the following during the study: hospitalization or prolongation of hospitalization due to HZ, disseminated HZ (including disseminated HZ rash or VZV viremia), visceral HZ, ophthalmic HZ, neurological impairment due to HZ, or administration of intravenous acyclovir therapy for treatment of HZ in adults with HM.
5. To assess the impact of V212 on the development of PHN. PHN is defined as a worst pain score (in the previous 24 hours) of 3 or greater (0-to-10 scale) on the ZBPI, that persists or appears greater than or equal to 90 days after the onset of HZ rash in adults with HM.
6. To assess the immunogenicity of V212 in adults with STM or HM.
7. To describe the impact of HZ on activities of daily living (ADL) and quality of life (QoL), and to assess the impact of V212 on interference with ADL and QoL in study patients who develop HZ.
8. To describe HZ-related non-protocol-mandated health care resource utilization (HCRU), and assess the impact of V212 on HZ-related non-protocol-mandated HCRU, and work and productivity loss (WPQ).
9. To assess the impact of V212 on the severity and duration of HZ-related pain.
10. To assess the impact of V212 on the severity of HZ rash including the extent of rash, number of skin lesions present, and number of dermatomes involved.
11. To assess the association of immunogenicity at postvaccination with the risk of HZ in adults with STM or HM.

The exploratory objectives (1)-(5) will be evaluated for HM only; objectives(6)-(10) will be evaluated for STM and HM separately and (11) will be evaluated in both combined STM and HM populations and individual subpopulation.

## **2.2 PATIENT INCLUSION CRITERIA**

An individual will be eligible to participate in this study if all of the following criteria apply:

1. Patient has been diagnosed with a solid tumor or hematologic malignancy AND is not likely to undergo hematopoietic cell transplant (HCT) and meets one of the criteria specified below.
  - Is 18 years of age or older and is receiving a cytotoxic or immunosuppressive chemotherapy regimen.

OR

- Is 50 years of age or older\* with a hematologic malignancy, not in remission, regardless of whether the patient is or is not receiving chemotherapy.

\* **Note: In India only, enrollment is restricted to patients 18 to 65 years of age.**

2. Life expectancy  $\geq$  12 months.
3. Signed an informed consent prior to any study procedures.
4. Patient has prior history of varicella, antibodies to VZV (documented prior to receipt of blood products), or residence (for  $\geq$ 30 years) in a country with endemic VZV infection, or if participant is <30 years old, attended primary or secondary school in a country with endemic VZV infection (see Section 3.2.8 for more details).
5. All female patients of childbearing potential (as defined below under #7) must have a negative serum or urine pregnancy test (sensitive to 25IU  $\beta$ -hCG).
6. Able to understand and complete study questionnaires.
7. Patient is highly unlikely to conceive during the time period starting 2 weeks prior to enrollment through 6 months from last vaccination dose, as indicated by at least one “yes” answer to the following questions:
  - Patient is male.
  - Patient is female who agrees to remain abstinent or use (or have their partner use) adequate contraception during the time period starting 2 weeks prior to enrollment through 6 months from the last vaccination dose. Note that simultaneous use of two reliable forms of contraception is recommended.
  - Patient is a female who is not of reproductive potential. A female patient who is not of reproductive potential is defined as: one who has either (1) reached natural menopause (defined as 6 months of spontaneous amenorrhea with serum follicle stimulating hormone [FSH] levels in the postmenopausal range as determined by a laboratory, or 12 months of spontaneous amenorrhea), (2) post-surgical bilateral oophorectomy and/or hysterectomy, or (3) bilateral tubal ligation.
8. Patients with STM will be eligible for enrollment if they have not received (nor are expected to require receipt of) blood products within 3 months prior to enrollment through 28 days Postvaccination 4.

## **2.3 PATIENT EXCLUSION CRITERIA**

An individual will not be eligible to participate in this study if any of the following criteria apply:

1. A history of allergic reaction to any vaccine component (including gelatin) or an anaphylactic/anaphylactoid reaction to neomycin (a history of contact dermatitis to neomycin is not a criterion for study exclusion).
2. Prior history of HZ within 1 year of enrollment.
3. Prior or expected receipt of any varicella or non-study zoster vaccine.
4. Patient is currently receiving or expected to receive long-term antiviral prophylaxis (greater than 4 weeks duration) with activity against herpes simplex virus (HSV), VZV or cytomegalovirus (CMV).
5. Patient is pregnant or breastfeeding or expecting to conceive within the period of 2 weeks prior to enrollment throughout 6 months after last vaccination dose.
6. Any live virus vaccine administered or scheduled in the period from 4 weeks prior to Dose 1 through 28 days postvaccination dose 4.
7. Any inactivated vaccine administered or scheduled within the period from 7 days prior to, through 7 days following, any dose of study vaccine.
8. Unlikely to adhere to the study procedures or attend study visits.
9. Any other reason that in the opinion of the investigator might interfere with the evaluation required by the study.
10. Patients with STM will be excluded from study if they have received (or are expected to require receipt of) blood products within 3 months prior to enrollment through 28 days Postvaccination 4.

### **2.3.1 Deferment Criteria (Prior to Vaccination of Doses 2 through 4)**

NOTE: SPONSOR must be notified of deferment. At sites located in the United States, site personnel should contact one of the study personnel listed on the Sponsor Contact page in the Administrative Binder. Internationally, the site should contact the local Merck subsidiary monitor.

1. The patient has an acute illness that requires active medical intervention or monitoring to avert serious danger to the participant's health or well-being and, in the opinion of the investigator, may interfere with the evaluation of the study objectives. (The maximum amount of time for which the vaccination should be deferred is 30 additional days).

2. The patient has received an inactivated vaccine such as the influenza vaccine. In that case, administration of the study vaccination should be deferred for 7 days following receipt of the inactivated vaccine.

The deferment criteria noted above must be reviewed prior to each vaccination for Doses 2 through 4, to ensure that patients do not meet the criteria specified. If a participant meets any deferment criterion, this must be reported to the SPONSOR, and all study procedures with the exception of the administration of the vaccine/placebo should be conducted on the day the vaccination was deferred.

### **2.3.2 Continuation in the Study under Special Circumstances**

A patient should not receive additional doses of vaccine or placebo but should remain in the study to be followed for safety, efficacy and immunogenicity if:

- The patient develops a severe allergic reaction to a component of the vaccine (i.e., swelling of the mouth and throat, difficulty breathing, hypotension or shock) following administration of the prior vaccine dose.
- The patient becomes pregnant.
- The patient undergoes hematopoietic cell transplant (HCT).

## **2.4 STUDY DESIGN AND DURATION**

### **2.4.1 Summary of Study Design**

This is a randomized, double-blind (with in-house blinding procedures), placebo-controlled, multicenter study to evaluate the efficacy, immunogenicity, safety and tolerability of V212 in adults with STM or HM. The study will enroll patients who are 18 years of age and older who have either STM or HM and are receiving chemotherapy. **(Note: In India only, enrollment is restricted to patients 18 to 65 years of age.)** In addition, patients 50 years of age and older who have HM, not in remission, will be enrolled regardless of whether they are receiving chemotherapy. **(Note: In India only, patients 50 to 65 years of age who have HM, not in remission, will be enrolled regardless of whether they are receiving chemotherapy.)**

Approximately 5264 patients (~2632 in the vaccine group; ~2632 in the placebo group), 18 years of age or older will be randomized to receive either V212 or placebo given as a 4-dose regimen administered ~30 days apart. **(Note: In India only, enrollment is restricted to patients 18 to 65 years of age.)** Randomization will be stratified by baseline medical condition with approximately 2696 patients with STM (receiving chemotherapy) and 2568 patients with HM enrolled into the study. Patients with HM will be further stratified into one of two strata, low immunocompromise (IC) or moderate to high IC, based on the patient's HM diagnosis and/or chemotherapeutic regimen (see Appendix 6.1). The planned randomization schedule by vaccination group is shown in Section 2.4.2. Enrollment for this study is expected to be completed in approximately 36 months.

This is an event-driven study based upon the occurrence of confirmed HZ cases. The combined dropout rates and the combined HZ event rates will be monitored on an ongoing basis using the blinded database. Patients will remain in the study from the time of enrollment until accrual of the targeted number (~90) of confirmed HZ cases in the STM population.

The planned study duration stated in this protocol is estimated based upon assumptions related to enrollment rate and follow-up time and HZ incidence in these populations. If these assumptions are met, the study will continue for approximately 5 years in order to accrue approximately 90 confirmed HZ cases. However, it should be noted that:

- Study duration may be less than or more than 5 years, depending upon the time it takes to accrue the necessary number of confirmed cases.
- The HZ event rates will be monitored on an ongoing basis using the blinded database. If the observed HZ case accrual rate indicates that more than 5 years of patient follow-up will be necessary to accrue the targeted number of confirmed cases, then the SPONSOR will declare the trial infeasible and terminate the study after approximately 5 years of patient follow-up have occurred, from the date the first patient is enrolled.

This study will use an adaptive design based on pre-specified vaccine efficacy criteria, using an independent, external DMC. There will be one interim analysis and one final efficacy analysis. The interim analysis will consist of a futility analysis for each individual subgroup (HM and STM).

The interim (futility) analysis was conducted when at least 50% of the total number of required confirmed HZ cases had accrued in each patient population, HM and STM. The interim analysis was conducted on 29-Oct-2014 for both populations. Results of the analysis were reviewed by the DMC, who made recommendations to the Steering Committee (SC) to end the study in the HM population and continue the STM arm only.

Patients will be monitored for HZ for the entire duration of the study. To that end, patients will be educated on the signs and symptoms of HZ and instructed to call the study site immediately if such symptoms develop, to arrange an evaluation by a medically qualified investigator (medically qualified is defined as physician, or in accordance with local regulations, a nurse practitioner or physician assistant). In addition, monthly efficacy contact by telephone, via the internet, or during a follow-up visit will be required for each patient until study completion, to determine if unreported HZ symptoms occurred.

It is important to note that HZ presentation in immunocompromised patients may be atypical, for instance with cases of rash over several dermatomes. Also, occurrence of severe complications is not uncommon. Finally, visceral involvement is possible and HZ can occur without a rash. In such cases, detection of VZV in diagnostic specimens from blood, cerebrospinal fluid (CSF), lung, liver or other organ may be a key element of the diagnosis of HZ. More information about identification of suspected HZ cases can be found in Section 3.2.17.2.

The follow-up of patients with suspected HZ (outlined in the flowchart in Section 1.8) will include the following steps:

- *Initial evaluation by a medically qualified investigator* – All patients with suspected HZ will be assessed by a medically qualified investigator as soon as possible after HZ symptom onset. During this first evaluation, samples for VZV PCR testing will be collected from skin lesions in patients with a HZ or HZ-like rash. In addition, blood samples for VZV PCR testing will be collected from all patients.
- *Continued monitoring by a medically qualified investigator until no new lesions or symptoms of HZ appear* – Patients will be subsequently assessed every 3-5 days by a medically qualified investigator until no new lesions appear and no new acute HZ symptoms appear. Subjects with a rash should be assessed for rash evolution and the signs and symptoms of the development of HZ-associated complications, and any relevant laboratory findings should be reported. For subjects without a rash, clinical findings and any relevant laboratory and radiologic results should be reported. Severity of HZ-related pain, the development of HZ-associated complications, interference with activities of daily living, functional health status, quality of life, HZ-related healthcare utilization and effect on work/productivity will be assessed through the use of interview questionnaires administered by site personnel.

*Monthly follow-up assessment over a 6-month period* – Patients will also undergo serial (monthly) assessments over the 6 months following the initial report of suspected-HZ to capture the progression and resolution of disease characteristics such as severity of HZ-related pain, the development of HZ-associated complications, interference with activities of daily living, functional health status, quality of life, HZ-related healthcare utilization and effect on work/productivity. These assessments will be conducted through the use of interview questionnaires administered by site personnel (WPQ, HCU), or completed by the patient (ZBPI, European Quality of Life [EurQoL/EQ5D]) as indicated. Patients with a suspected case of HZ who have pain persisting longer than 6 months should continue in HZ follow-up until the pain resolves or the study ends.

The summary of clinical findings, including any results of non-study laboratory and radiologic assessments conducted locally to support the HZ diagnosis, and results from the blood VZV PCR testing will be provided to the Clinical Adjudication Committee (CAC).

Another important goal of the study is to evaluate the safety and tolerability of V212 in the HM and STM patient populations. Adverse experiences will be collected from Visit 1 through Visit 5 using a Vaccination Report card (VRC). All subjects will receive a VRC at each vaccination visit (Visits 1 through 4). The VRC will be used to collect safety information between each vaccination period (minimum 20 days postvaccination dose 1 through 3, through 28 days postvaccination dose 4). The VRC will be returned by the patient and reviewed by study site personnel at the next scheduled study visit.

Serious adverse experiences (SAE) will be collected, regardless of causality, for the entire duration of the study. Patients will be instructed to call the study site immediately, at any time during the study, if they develop an adverse experience that meets SAE criteria. In addition patients undergo periodic safety follow-up to assess whether they developed a clinical adverse experience that met SAE criteria since their last contact with site personnel. As indicated in the Study Flow Chart (Section 1.7), such safety follow-ups will occur at each scheduled study visit (Visit 1 through 5) and, after Visit 5, by telephone Periodic Safety Contact (approximately every 3 months, beginning 3 months following Visit 5, and continuing every 3 months for the duration of the study).

A pregnancy test will be performed on all female patients of childbearing potential at Visits 1, 2, 3, and 4 prior to vaccine administration. Any female patient with a positive pregnancy test at Visit 1 will not be vaccinated and will not be allowed to participate in the study. Female patients with a positive pregnancy test after Visit 1 will not receive additional doses of V212 or placebo, but will remain in the study to be followed for safety, efficacy and immunogenicity.

To ensure that no alarming, unusual, or unexpected safety problems are occurring with the vaccine in the HM or STM populations, safety will be monitored during the study by the same independent, external DMC that will monitor the interim futility and efficacy analyses. The DMC will periodically evaluate interim safety and efficacy data and will provide periodic recommendations to the SC, to continue, modify, or stop the clinical trial. See section 3.2.21 for more details about the DMC and SC.

Overall, the study may be ended in the following situations:

- 1) When the required number of confirmed HZ cases has accrued; or
- 2) If the decision is made to end the study early following a recommendation made by the DMC based on safety concerns; or
- 3) If the observed HZ case accrual rate indicates that more than 5 years of patient follow-up will be necessary to accrue the targeted number of confirmed cases, then the SPONSOR will declare the trial infeasible and terminate the study after approximately 5 years of patient follow-up have occurred, from the date the first patient is enrolled

In any of these situations, the study will begin to enter the close-out phase, and no additional suspected cases of HZ will be accrued beyond the date for initiation of close-out procedures, as provided in the Close-Out Standard Operating Procedures (SOP) and patients already entered into the suspected HZ-follow-up will complete their 6-month assessment periods. All patients will be contacted to complete the study close-out questionnaire. Details of the close-out procedures will be provided in the Close-Out SOP. In the event the study ends sooner than 1 year after the last vaccine dose is administered, the study will continue to follow all patients for safety and efficacy until all patients have completed 1 year of follow-up.

The clinical, statistical and data management study personnel at the SPONSOR who are involved with study conduct will remain blinded to subject vaccination group allocations until the required number of cases of the primary efficacy endpoint have been observed, study close-out procedures have been completed, data discrepancies have been addressed, and the database is unblinded for the primary efficacy analysis.

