## 1.4 SUMMARY OF STUDY DESIGN

Approximately 5264 patients (~2568 HM patients; ~2696 STM patients), 18 years of age or older will be equally randomized to receive a 4-dose regimen of either V212 or placebo. (**Note: In India only, enrollment is restricted to patients 18 to 65 years of age.**) Patient allocation will be double-blinded, with in-house blinding procedures. Enrollment for this study is expected to be completed in approximately 36 months. Study duration is anticipated to be approximately 5 years from the date the first patient is enrolled.

This is an event-driven study based upon the occurrence of confirmed HZ cases. HZ rates will be monitored on an ongoing basis using the blinded database. The primary efficacy analysis will be conducted after at least 90 confirmed HZ cases have been accrued in the STM population. Patients will remain in the study from the time of enrollment until accrual of the targeted number (~90) of confirmed HZ cases. This study uses an adaptive design based on pre-specified criteria, using an independent, external Data Monitoring Committee (DMC) to monitor safety and efficacy. The study will be conducted based on 2 key efficacy milestones as listed below:

- When at least 50% of the required confirmed HZ cases have accrued for each population, HM and STM, interim futility analysis will be conducted for each group (completed 29-Oct-2014).
- When 90 confirmed HZ cases have accrued in the STM population, the database will be unblinded and the final efficacy analysis will be conducted. Of note, if the observed HZ case accrual rate indicates that more than 5 years of patient follow-up will be necessary to accrue the targeted number of confirmed cases, then the SPONSOR will consider it beyond the adjustment cap and terminate the study after approximately 5 years of patient follow-up have occurred (from the date the first patient is enrolled).

During the interim analysis, a futility analysis was conducted to assess whether efficacy met a pre-specified level. The analysis was conducted separately for each patient population (HM and STM) when at least 50% of required HZ cases had accrued in the corresponding population (29-Oct-2014). Analysis results were evaluated by the DMC with the following outcome:

HM population: solid statistical evidence of futility for the primary endpoint. Thus, enrollment and vaccination was stopped on 04-Nov-2014 and study close-out procedures in this population began on 19-Nov-2014.

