#### 2.7.4 Power and Sample Size

This is an event-driven study. With a 1:1 randomization ratio between the vaccine and placebo groups and a total of 90 HZ cases in the STM population with 2696 patients, the study will have an overall power of ~84.2% to detect  $65\% \text{ VE}_{\text{HZ}}$  at the overall two-sided 0.025 significance level, based on the success criterion of the lower bound 97.5% CI for  $\text{VE}_{\text{HZ}}$  being greater than 25%.

To accrue ~90 confirmed HZ cases in the STM population during the time period from enrollment through approximately the end of maximum 5 years postvaccination, enrollment of approximately 2696 patients (1348 receiving vaccine and 1348 receiving placebo) will be required, assuming 1) 30% total lost-to-follow-up, 2) an HZ rate of 17 per 1000 in the placebo group for STM, 3)  $\text{VE}_{\text{HZ}}=65\%$  for STM, and 4) 36 months of study enrollment. The sample size calculation follows the methods described in Lachin [21].

The dropout rates and the combined HZ event rates will be monitored on an ongoing basis using the blinded database. If ongoing blinded pooled event rate monitoring indicates that there may be fewer than 90 confirmed cases of HZ accrued for the STM population, then the follow-up time may be extended. More specifically, if the observed HZ case accrual rate indicates that more than 5 years of patient follow-up will be necessary to accrue the targeted number of confirmed cases, then the SPONSOR will consider it beyond the adjustment cap and terminate the study after 5 years of patient follow-up have occurred.

A subset of patients will participate in the ELISPOT substudy. Power and sample size of the ELISPOT substudy is discussed in Section 3.5.7.3.

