## **3.5 STATISTICAL ANALYSIS PLAN**

This section outlines the statistical analysis strategy and procedures for the study. If, after the study has begun, but prior to any unblinding, changes are made to primary and/or key secondary hypotheses, or the statistical methods related to those hypotheses, then the protocol will be amended (consistent with ICH Guideline E-9). Changes to exploratory or other non-confirmatory analyses made after the protocol has been finalized, along with an explanation as to when and why they occurred, will be listed in the Clinical Study Report (CSR) for the study. Post hoc exploratory analyses will be clearly identified in the CSR. No separate Statistical Analysis Plan (SAP) will be issued for this study.

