### **3.5.1 Responsibility for Analyses**

The statistical analysis of the data obtained from this study will be the responsibility of the designee/Clinical Biostatistics department of the SPONSOR.

This study will be conducted as a double-blind study under in-house blinding procedures. The official, final database will not be unblinded until medical/scientific review has been performed, protocol violators have been identified, and data have been declared final and complete.

This study is event-driven, with one interim futility analysis and one final efficacy analysis. The interim analysis included futility analyses for individual subgroups (HM and STM). The interim futility analysis was done when at least 50% of the total number of required evaluable HZ cases in each patient population, HM and STM, had accrued. More specifically, the futility analysis was conducted on the HM population when at least 68 cases had accrued in the HM subgroup and the futility analysis was conducted on the STM population when at least 48 cases had accrued in the STM subgroup.

The DMC will monitor safety periodically and will be responsible for reviewing the results of the planned formal interim analyses. The DMC may recommend stopping the study early based on safety concerns or futile efficacy results from the interim futility analysis (see Section 3.5.8.1 and DMC guidelines).

An unblinded SPONSOR statistician who is otherwise unrelated to this protocol will serve as a non-voting member of DMC and will be responsible for performing these preliminary/interim analyses for DMC. Detailed implementation of the interim analysis is described in the DMC charters (separate documentation).

All the interim analysis data will remain blinded to SPONSOR study personnel, the study investigator, the laboratory staff, the CAC members, and the patients throughout the study, until the final database unblinding when all required evaluable HZ cases are accrued.

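### Does a stop at the 5-year cap with fewer than 90 solid-tumour cases leave the primary test without a rule?

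*Combined protocol and SAP*

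**What the plan says.** Three places tie the analysis or the unblinding to the case count.

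- Section 1.4: "The primary efficacy analysis will be conducted after at least 90 confirmed HZ cases have been accrued in the STM population".
- Section 2.4.1: sponsor study personnel stay blinded "until the required number of cases of the primary efficacy endpoint have been observed", close-out is complete and data queries are settled.
- Section 3.5.1: interim data stay blinded "until the final database unblinding when all required evaluable HZ cases are accrued".

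The cap appears in Sections 1.4, 2.4.1, 2.7.4 and 3.5.7.1. Section 2.4.1 puts it this way: if the target cannot be met in time, "then the SPONSOR will declare the trial infeasible and terminate the study after approximately 5 years of patient follow-up have occurred", counted from first enrolment. Section 2.7.4 has the shorter "terminate the study after 5 years of patient follow-up have occurred", with no starting point. After such a stop, Sections 1.4 and 2.4.1 prescribe close-out and no new suspected cases. Section 2.4.1 adds that open cases finish their 6-month follow-up, and both sections keep the one-year minimum after the last dose.

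Other places set the time of the test without a count. Section 2.1.2 states: "The following hypothesis will be tested at the end of the study in the STM population". Section 3.5 adds: "No separate Statistical Analysis Plan (SAP) will be issued for this study".

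**The concern.** Read alone, the count-based sentences make 90 cases a precondition for unblinding and for the primary test. The cap then creates an ending in which that precondition is never met, and calling the trial infeasible could suggest that no confirmatory test follows. Section 3.2.19, on study completion, does not list the cap among its triggers. With no separate analysis plan to come, the sponsor might have to settle the status of the primary result after the final count is known. A decision taken that late can be challenged, and the scenario is not remote on the plan's own planning figures.

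**Working it through.** **1. Reproduce the stated power.** Inputs from Sections 2.1.2 and 3.5.7.1: 1:1 allocation, 90 cases, success if the lower confidence bound for efficacy exceeds 25% at one-sided 0.0125. Given D cases in total, the vaccine-arm count is binomial with share (1 − VE)/(2 − VE).

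- Null share: 0.75/1.75 = 0.4286. Share at VE 65%: 0.35/1.35 = 0.2593.
- For D = 90, the largest vaccine count with null tail probability at or below 0.0125 is 27 (tail 0.0083).
- P(X ≤ 27) at share 0.2593 is 84.2%. The same limit gives 99.9, 99.2, 95.0, 84.2, 66.6 and 46.7% for VE 80 down to 55, which is all of Table 3-3.

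**2. Cases expected at the cap.** Inputs from Section 3.5.7.1: 1348 per arm, placebo rate 17 per 1000 (taken as person-years), VE 65%, 36 months of enrolment, 30% total loss. Assumptions: uniform enrolment, exponential events and loss, and loss hazard η = −ln(0.7)/L, where L is the time by which 30% are lost. The plan does not give L.

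Per arm, with m = λ + η and 5 years from first enrolment:

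cases = 1348 × (λ/m) × [1 − (e^(−2m) − e^(−5m))/(3m)]

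For L = 5, η = 0.0713. Placebo (λ = 0.017) gives 68.4 and vaccine (λ = 0.017 × 0.35 = 0.00595) gives 24.4, in total 92.9 before rounding. Poisson tails give the probabilities:

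| Loss pattern | Expected cases | P(≥ 90) | P(75–89) | P(< 75) |
|---|---|---|---|---|
| none | 105.5 | 0.94 | 0.06 | < 0.01 |
| 30% by 5 years | 92.9 | 0.63 | 0.34 | 0.03 |
| 30% by 4 years | 90.0 | 0.52 | 0.44 | 0.05 |
| 30% by 3.5 years | 88.1 | 0.43 | 0.50 | 0.07 |
| 30% by 3 years | 85.6 | 0.33 | 0.56 | 0.11 |

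If the cap meant 5 years for each patient, the middle three rows would give 125.9, 120.8 and 117.4 cases, and P(≥ 90) would exceed 0.99.

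**3. What a test on fewer cases costs.** The method of step 1, at VE 65%:

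| Cases | Vaccine limit | Exact type I error | Power | Observed VE at limit |
|---|---|---|---|---|
| 90 | 27 | 0.0083 | 84.2% | 57.1% |
| 89 | 27 | 0.0104 | 85.7% | 56.5% |
| 85 | 25 | 0.0075 | 80.6% | 58.3% |
| 80 | 24 | 0.0125 | 83.2% | 57.1% |
| 77 | 22 | 0.0069 | 74.9% | 60.0% |
| 75 | 22 | 0.0112 | 79.2% | 58.5% |
| 60 | 16 | 0.0071 | 61.8% | 63.6% |

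Over 75 to 89 cases power averages 81.1%. It is not monotone because the count is discrete. Type I error is at or below 0.0125 at every count from 60 to 90. The planned test is a stratified Cox model, so these figures approximate it.

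**4. Is there a default for a cap stop?**

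- Section 2.4.1 lists the cap as the third way the study may end.
- Section 2.1.2 puts the test at the end of the study.
- Section 2.4.1, just after the cap bullet, announces one interim and one final efficacy analysis, unconditionally.
- Section 3.5.6 tests the primary hypothesis at one-sided 0.0125, with no count.
- Section 3.5.5.1.1 censors at the date HZ surveillance stops, which works for any count.
- Section 3.2.18 ends blinding when follow-up, data screening and the identification of violators are complete. The second paragraph of Section 3.5.1 is similar. Neither names a count.

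Together these give one course: at study end, by whichever route, lock, unblind and test once at 0.0125.

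**The case for a change.** The best case for a change is that none of the supporting sections mentions a shortfall, and that they do not match the count-based triggers in Sections 1.4, 2.4.1 and 3.5.1. A single sentence would remove the doubt at no cost in patients or follow-up. The mismatch is real, and so is the chance of a shortfall.

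It does not follow that the analysis lacks a route. No sentence withholds the test below 90, and in Section 1.4 the cap is described inside the final-analysis milestone. Section 3.5 also provides for a protocol amendment if primary hypotheses or methods change before unblinding, so the absence of a separate analysis plan does not close the matter. A decision at the cap would rest on calendar time and a pooled, blinded count, so it would not be informed by the treatment comparison.

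The probabilities in the working start from zero cases. This amendment followed an interim analysis triggered at 48 or more STM cases, and its summary of changes cites projected STM accrual among the reasons. The chance of a shortfall as it then stood cannot be found from the documents.

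A much larger shortfall would cost real power (61.8% at 60 cases). That is the price of the cap, and a sentence about the test would not recover it.

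**Conclusion.** The concern does not call for a change. The wording is uneven: some sections speak of the required cases and others of the end of the study, and neither group names the cap. Read together, they lead to one primary test at one-sided 0.0125 on all first confirmed cases up to the end of surveillance, whichever limit comes first. The test level is unaffected, and for 75 to 89 cases mean power falls from 84.2% to 81.1%, about 3 percentage points.

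The remaining oddities are clerical. Some statements of the cap omit its starting point. The remarks on extending follow-up in Sections 2.4.1, 2.7.4 and 3.5.7.1 differ. Section 3.5.7.1 still allows for added enrolment that Section 3.1.2 rules out for the STM population.

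The conclusion assumes that the cap runs from first enrolment, that the 17 per 1000 is per person-year, and that the exact binomial calculation approximates the Cox test. The reading of the sections does not depend on the loss pattern.
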